8.1.1 Part A SAD, Healthy Volunteers

Subjects will be admitted to the clinical research unit (CRU) on the day prior to (first) drug administration (Day -1). Following drug administration of a single dose of BMS-986251 on Day 1, they will remain in the CRU for close observation until discharge from the CRU on Day 7 (144 hours post-dose). Subjects will return for ambulatory assessments on Days 9 and 11, including follow-up assessments on Day 11.

Subjects enrolled in the BA/FE cohort will return to the CRU for a 2nd and 3rd study period. Washout between single dose administrations will be at least 2 weeks, based on an anticipated terminal half-life of BMS-986251 of approximately 40 hours. The design of the 2nd and 3rd study period is the same as the first period, with a mandatory in-clinic stay from Day -1 to Day 7 and ambulatory visits on Days 9 and 11. Subjects will be dosed on Day 1 of each period. Follow-up assessments will be performed on Day 11 of Period 3 only; on Day 11 of Period 1 and 2 limited assessments including blood sampling for PK and PD (PD only in Period 1) will be performed. Please refer to the procedural outline in Table 1 to see which assessments are to be performed at each visit.

The planned single dose treatments are provided in Table 6. Eight healthy subjects will be assigned to each of 6 planned SAD cohorts and the BA/FE cohort. Subjects will be randomized within each of the SAD cohorts to receive a single oral dose of BMS-986251 or a matched placebo in a ratio of 3:1. All subjects in the BA/FE cohort will receive BMS-986251. In the first SAD cohort, sentinel dosing will be employed (see Section 8.1).

Within each cohort, safety, tolerability, PK, and PD assessments will be performed at predefined time points. Following completion of each dose cohort there will be a review of blinded study data prior to dose escalation by the Sponsor's dose escalation review group. This group will include the Investigator, PRA Medical Monitor, the BMS Study Director, and additional personnel as deemed necessary by the Sponsor (such as a pharmacokineticist). SAD dose escalation decisions will be based on the safety, tolerability and PK results of the ongoing cohort up to and including Day 7, and on the PD results up to and including Day 5. Medication administration in the next dose cohort will not start until at least 6 subjects have been dosed in the previous dose cohort and the data have been reviewed. The dose escalation

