9.3 Endpoints

9.3.1 Primary Endpoints

The primary objective to assess the safety, tolerability and PK of single and multiple oral doses of BMS-986251 in healthy subjects and in patients with moderate-to-severe psoriasis will be measured by the following primary endpoints:

Safety and tolerability

- Number and percent of subjects that experience the following: SAE, death or an AE leading to study discontinuation, during the study participation or up to 1 month post discontinuation of dosing or last participation in the study for SAE.
- Number and percent of subjects with potentially clinically significant changes in ECG parameters, vital signs, or clinical laboratory parameters from Day 1 through the final follow visit.

Other safety measures collected during the study are not considered among the primary endpoint and will be summarized as safety endpoints. Stopping rules for safety are discussed in Section 8.3.5.5.

Pharmacokinetics

PK parameters will be derived from BMS-986251 concentration versus time data measured at the time points specified in the schedule of assessments for each part of the study. The PK parameters to be assessed are listed in Section 8.5.3. The PK parameters to be evaluated in each part include but are not limited to the following:

- Part A: C_{max} , t_{max} , AUC_{0-t} , AUC_{0-inf} , $t_{1/2}$, CL/F , V_z/F , Ae_t , $Fe_{urine}\%$, CL_R
- Part B:
Day 1: C_{max} , t_{max} , AUC_{0-t} , AUC_{0-24}
Days 2-14: C_{pre}
Day 14: C_{max} , t_{max} , AUC_{0-t} , AUC_{0-24} , CL/F , V_z/F , $t_{1/2}$, $AR_{AUC0-24}$, $AR_{C_{max}}$, Ae_t , $Fe_{urine}\%$, CL_R
- Part C (intensive PK sampling sub-cohort):
Day 1: C_{max} , t_{max} , AUC_{0-t} , AUC_{0-24}

- Days 2-14: C_{pre}
- Day 14: C_{max} , t_{max} , AUC_{0-t} , AUC_{0-24} , CL/F , V_z/F , $t_{1/2}$, $AR_{AUC_{0-24}}$, $AR_{C_{max}}$
- Part C (sparse PK sampling sub-cohort):
Days 7 and 14: C_{pre}

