**Table 4 Plasma BMS-986251 PK Parameters- Part A (SAD Part)**

Parameter	SAD Part	MAD Part Day 1*	Description	SAS Programming Notes
Cmax	X	X	Maximum plasma concentration. Observed peak analyte concentration obtained directly from the experimental data without interpolation, expressed in concentration units	Cmax from WNL
Tmax	X	X	Time to maximum plasma concentration. First observed time to reach peak analyte concentration obtained directly from the experimental data without interpolation, expressed in time units.	Tmax from WNL
AUC(0-T)	X	X	Area under the concentration-time curve (time 0 to time of last quantifiable concentration).	AUClast from WNL
AUC(INF)	X	X	Area under the plasma concentration-time curve (time 0 to infinity). A valid half-life is required to retain this parameter.	AUCINF_obs from WNL If T-HALF is present.
AUC%Extrap	X	X	Percentage of the AUC(INF) that is extrapolated.	AUC_%Extrap_obs from WNL– Listed only
T-HALF	X	X	Terminal phase half-life expressed in time units. A valid Lz is required to retain.	HL_Lambda_z from WNL
Lz	X	X	Terminal phase rate constant calculated by the WinNonlin generated best fit linear regression of the terminal log-linear portion of the concentration vs. time curve. Linear regression of at least 3 points and an adjusted R2 > 0.80 are required to retain.	Lambda_z from WNL.
CL/F	X	X	Apparent clearance	CL_F_obs from WNL
Vd/F	X	X	Apparent volume of distribution at terminal phase	Vz_F_obs from WNL
Adj R 	X	X	Adjusted R  value of terminal elimination phase	Rsquared adjusted from WNL – Listed only

Parameter	SAD Part	MAD Part Day 1*	Description	SAS Programming Notes
Lz_Start	X	X	The time point starting the log-linear elimination phase defining their terminal half-life	Lambda_z_lower from WNL – Listed only
Lz_End	X	X	The time point ending the log-linear elimination phase defining the terminal half-life	Lambda_z_upper from WNL – Listed only
Lz_N	X	X	Number of time points in the log-linear elimination phase defining the terminal half-life	No_points_lambda_z from WNL – Listed only

Note: AUCs will be calculated using linear up / log down, expressed in units of concentration x time.

\* There are only 2 subjects in cohort B1 who have been dosed till Day 10. PK parameters will be calculated for Part B (MAD part) Day 1 if feasible.

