**Table 9 Pharmacokinetic Sampling Schedule; Part B**

Sample Collection Time		Time (relative to dosing) hour:min	Blood Sample	Urine Sample	
Study Day	Time (event)		PK Blood Sample	Collection Interval	
-1	NA	NA		X	
1	0 h (pre-dose)	00:00	X		
1	0.5 h	00:30	X		
1	1 h	01:00	X		
1	1.5 h	01:30	X		
1	2 h	02:00	X		
1	3 h	03:00	X		
1	4 h	04:00	X		
1	6 h	06:00	X		
1	8 h	08:00	X		
1	12 h	12:00	X		
2-13	0 h (pre-dose)	0:00	X		
2-13	4 h	4:00	X		
14	0 h (pre-dose)	0:00	X	X (0-24 h on Day 14)	
14	0.5 h	00:30	X		
14	1 h	01:00	X		
14	1.5 h	01:30	X		
14	2 h	02:00	X		
14	3 h	03:00	X		
14	4 h	04:00	X		
14	6 h	06:00	X		
14	8 h	08:00	X		
14	12 h	12:00	X		
15	24 h	24:00	X		
16	48 h	48:00	X		
18	96 h	96:00	X		
20	144 h	144:00	X		
24	240 h	240:00	X		

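### SAP Table 4 allows half-life, AUC(INF), CL/F and Vd/F from a 24 h Part B Day 1 profile, with no limit on extrapolation (low impact)

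*SAP*

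**What the plan says.** - **Which parameters.** SAP Table 4 (section 15.1.1.2) has a column for MAD Day 1. It is marked for Cmax, Tmax and AUC(0-T), and also for AUC(INF), AUC%Extrap, T-HALF, Lz, CL/F, Vd/F and the regression diagnostics. There is no AUC(0-24) row. The footnote notes that cohort B1 has only two subjects, dosed to Day 10, and that "PK parameters will be calculated for Part B (MAD part) Day 1 if feasible". Feasibility is not defined.
- **Retention rules.** For Lz: "Linear regression of at least 3 points and an adjusted R2 > 0.80 are required to retain". For AUC(INF): "A valid half-life is required to retain this parameter". AUC%Extrap, described as "Percentage of the AUC(INF) that is extrapolated", is listed only and triggers nothing. The SAP gives no minimum span in half-lives and no ceiling on extrapolation.
- **Sampling.** SAP Table 9 samples Part B to 12 h on Day 1, then pre-dose on Day 2, just before the second daily dose.
- **Half-life.** Protocol 8.1.1 gives an "anticipated terminal half-life of BMS-986251 of approximately 40 hours".
- **Protocol parameters.** For Part B Day 1, protocol 9.3.1 lists Cmax, tmax, AUC0-t and AUC0-24. It places CL/F, Vz/F and half-life on Day 14 and names AUC0-inf for no Part B day. Protocol 8.5.3 bases multiple-dose CL/F on Day 14 AUC0-24.
- **Declared changes.** SAP 3.0 undertakes to identify substantial differences from the protocol. SAP 7.1 does not mention the changed Day 1 set.

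**The concern.** A terminal slope fitted to 24 h of data covers only 0.6 of a 40 h half-life. AUC(INF), CL/F and Vd/F all inherit that slope, so most of AUC(INF) would come from the extrapolation and not from measured concentrations. The R2 rule measures how straight the fitted segment is. It does not show that the terminal phase was reached, or that enough of it was seen. The report could therefore list half-life, clearance and volume values for a first-in-human compound that the data cannot support, under a rule that calls them valid.

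The same gap applies to Part A, where AUC(INF) is one of three responses in the dose-proportionality power model (SAP 15.2.3.1). It would matter there only if low-dose profiles end early.

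**Working it through.** The documents state no extrapolated percentage for Part B Day 1, so there is no figure of theirs to reproduce first.

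**Inputs from the documents.** Half-life 40 h (anticipated); last Part B Day 1 sample at 24 h; last Part A sample at 240 h; SAP rules of at least 3 points, Cmax excluded, adjusted R2 > 0.80, linear-up/log-down AUC.

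**1. Span.** 24/40 = 0.6 half-lives.

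**2. Extrapolated share, log-linear decline:** 2^(-T/half-life).
- Part B, T = 24 h: 2^(-24/40) = 66.0%. At 20 h, 2^(-24/20) = 43.5%; at 60 h, 2^(-24/60) = 75.8%.
- If the Day 2 pre-dose sample were not used, T = 12 h: 2^(-12/40) = 81.2%.
- Part A, T = 240 h: 2^(-240/40) = 1.6%.
- A one-compartment oral model at 40 h, with an assumed absorption rate of 2 to 0.3 per h, gives 66.6% to 70.0% at 24 h.

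**3. Does the SAP rule screen such profiles out?** Simulation of the rule on the Part B Day 1 times, 5,000 profiles per setting. The error SD (log scale), absorption rate and two-phase shape are assumptions.

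| Model | Error | Profiles kept | Half-life kept, h (5th / median / 95th) | AUC(INF) ÷ truth (5th / median / 95th) |
|---|---|---|---|---|
| One compartment, 40 h | 5% | 78% | 29 / 40 / 62 | 0.78 / 0.99 / 1.42 |
| One compartment, 40 h | 10% | 45% | 22 / 35 / 76 | 0.63 / 0.90 / 1.73 |
| One compartment, 40 h | 15% | 30% | 18 / 31 / 88 | 0.54 / 0.80 / 1.90 |

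The median half-life falls from 40 to 31 h as error grows, because steeper fitted slopes pass the R2 rule more easily. With an assumed two-phase decline (4 h and 40 h), 67% to 100% of profiles pass at these error levels, with median half-life about 14 to 21 h and median AUC(INF) about 0.66 to 0.72 of the truth.

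**4. When would Part A be affected?** Extrapolation exceeds 20% when 2^(-T/40) > 0.20, that is, when the last quantifiable sample is before T = 40 × log2(5) = 93 h. SAP 15.2.2 treats BLQ values after the first quantifiable point as missing, so low-dose profiles can end earlier. The quantification limit is not given. As an illustration only, with proportional log-linear kinetics, the 30-fold range from 2 to 60 mg shifts the last quantifiable time by 40 × log2(30) = 196 h. If 60 mg were just quantifiable at 240 h, 2 mg would end near 240 − 196 = 44 h, with 2^(-44/40) = 47% extrapolated.

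**The case against.** There is a fair case that this hardly matters, and much of it stands.

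- **Conditional marks.** The footnote makes the Day 1 parameters subject to feasibility, so it is too strong to say that the SAP orders them. That stands. But the condition has no criterion, and the only written rules let many such profiles through.
- **The protocol's lists are open-ended.** Protocol 9.3.1 and 8.5.3 say the parameters are not limited to those named. A reader might infer that the SAP contradicts the protocol; it does not. The narrower point is that the Day 1 set differs and SAP 7.1 does not name the difference.
- **Exposure without extrapolation is still reported.** A reader might infer that leaving out AUC0-24 removes the only such measure. The documents do not support that: Cmax and AUC(0-T) are both marked for Day 1. AUC(0-T) is close to AUC0-24 if it runs to a quantifiable Day 2 pre-dose sample, though the SAP does not say where it is cut.
- **No Part A comparison is lost.** Neither the protocol's Part A list nor SAP Table 4 contains AUC0-24, so restoring it for Part B alone gives nothing to compare with.
- **Termination removed most uses of AUC0-24.** Accumulation ratios, Day 14 CL/F and Part B dose linearity cannot be done with one dose level stopped at Day 10. That stands.
- **The extrapolated percentage is listed.** A reader would see it beside the value. This helps, but the listed percentage comes from the same doubtful slope, and listing it sets no rule on whether the value is reported.
- **The Part A ceiling is a choice.** The 20% figure is a convention with no source in these documents, and 1.6% is expected with quantification to 240 h. Protocol 9.4.3 limits summaries to adequate PK profiles, but neither document says what makes a profile adequate.

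**Conclusion.** The point holds, at low severity. SAP Table 4 permits half-life, AUC(INF), clearance and volume from a profile covering 0.6 of the anticipated half-life, and its retention rules do not prevent their being reported. About 66% of AUC(INF) would be extrapolated. The 40 h half-life is anticipated, not observed, but even at 20 h the share is about 44%. The simulation results rest on assumed kinetics and error and serve only to show that the R2 rule is not a reliable screen; the 66% needs only the anticipated half-life, the sampling times and log-linear decline.

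A reader might infer that a primary PK analysis is compromised. The documents do not support that. At most two subjects are affected, and perhaps fewer, because cohort B1 includes placebo and the SAP does not give their allocation. SAP 7.1 names only disposition, demographics and adverse events for Part B summary tables, so these values should appear mainly in listings. The power model uses Part A only. For Part A, the missing ceiling is a possible weakness, with no demonstrated effect at any dose level.

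**What to change.** - **SAP Table 4, MAD Day 1 column.** Remove AUC(INF), AUC%Extrap, T-HALF, Lz, CL/F and Vd/F, with the regression diagnostics that serve only them. Add AUC(0-24) as in protocol 9.3.1, or state that AUC(0-T) on Day 1 is cut at the Day 2 pre-dose sample. Claim no 24 h comparison with Part A unless AUC(0-24) is derived there too.
- **SAP 7.1.** Add one line naming any remaining difference from the protocol's Day 1 list.
- **Part A safeguard, stated before database lock.** Set a ceiling for AUC%Extrap, for example 20%. Above it, AUC(INF), CL/F and Vd/F are listed and flagged but left out of summaries, and AUC(INF) is left out of the power model.

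The cost is a few table cells, one retention rule and one sentence. The downside is that some low-dose AUC(INF) values may be left out of the Part A summaries and power model; they would remain in the listings.

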## 15.1.2 Urine Variables

### 15.1.2.1 Amounts Excreted

- Amount of BMS-986251 excreted in urine (Ae)
  - Calculated as the urine volume times the urine concentration for each interval.

### 15.1.2.2 Parameters

- PK Parameters for BMS-986251 as defined in Table 5.

**Table 5 Urine Parameter –SAD Part**

Parameter	Description	SAS Programming Notes
Ae(0-T)	Total amount of drug excreted unchanged into urine to time t obtained by adding the amounts excreted over each collection interval.	Summation $i = 1$ to $n$ of (Concentration (ng/mL) $t_{i-1}-t_i$ *volume(mL) $t_{i-1}-t_i$ ) Parameter will be missing if data is missing for any prior individual time interval.
Ae	Total amount of drug excreted unchanged into urine to last time obtained by adding the amounts excreted over each collection interval.	Summation $i= 1$ to $n$ of (Concentration (ng/mL) $t_{i-1}-t_i$ *volume(mL) $t_{i-1}-t_i$ ) Parameter will be missing if data is missing for any individual time interval.
Fe	Fraction (%) of the administered dose excreted unchanged into urine	$Ae/XXmg$ (dose)*100
CLr	Renal clearance	$Ae(0-T)/AUC(0-T)$

---

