8.5.3 Pharmacokinetics

Pharmacokinetic variables will be the plasma concentrations and urine concentrations (Part A and B only) of BMS-986251 and derived PK parameters. The PK parameters to be assessed for BMS-986251 include but are not limited to the parameters given below. Some of the listed parameters may only be calculated for specific parts of the study; this includes the assessment of urinary excretion of parent compound and metabolites in urine, which may be limited to the higher dosed cohorts in Part A and B. The relevant PK parameters to be calculated for each study part and study day are listed in Section 9.3.1.

C_{pre}	Pre-dose plasma concentration
C_{max}	Maximum observed plasma concentration
t_{max}	Time of maximum observed plasma concentration
AUC_{0-t}	Area under the plasma concentration-time curve from time zero to time of last quantifiable concentration
AUC_{0-inf}	Area under the plasma concentration-time curve from time zero extrapolated to infinite time
AUC_{0-24}	Area under the concentration-time curve over 24 hours (one dosing interval)
$AR_{C_{max}}$	Accumulation ratio: ratio of C_{max} following last dose (Day 14) to C_{max} following first dose (Day 1)
$AR_{AUC_{0-24}}$	Accumulation ratio: ratio of AUC_{0-24} following last dose (Day 14) to AUC_{0-24} following first dose (Day 1)
k_{el}	Terminal elimination rate constant
$t_{1/2}$	Terminal elimination half-life, calculated as $0.693/k_{el}$
CL/F	Apparent (oral) clearance, calculated as dose/ AUC_{0-inf} for single dose (Part A, Day 1) or dose/ AUC_{0-24} for multiple dose (Part B and C, Day 14)
V_z/F	Apparent volume of distribution at terminal phase
Ae_t	Cumulative urinary excretion (of the unchanged drug) (Part A and B only)
$Fe_{urine}\%$	Amount excreted unchanged in urine (% of dose) (Part A and B only)
CL_R	Renal clearance (Part A and B only)

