### Appendix 3: Pharmacokinetic Sampling Schedule from Protocol

**Table 8 Pharmacokinetic Sampling Schedule; Part A**

Sample Collection Time		Time (relative to dosing) hour:min	Blood Sample	Urine Sample
Study Day	Time (event)		PK Blood Sample	Collection Interval
-1	NA	NA		X
1	0 h (pre-dose)	00:00	X	
1	0.5 h	00:30	X	X (0-12 h)
1	1 h	01:00	X	
1	1.5 h	01:30	X	
1	2 h	02:00	X	
1	3 h	03:00	X	
1	4 h	04:00	X	
1	6 h	06:00	X	
1	8 h	08:00	X	
1	12 h	12:00	X	X (12-24 h)
2	24 h	24:00	X	X (24-48 h)
2	36 h	36:00	X	
3	48 h	48:00	X	
4	72 h	72:00	X	X (48-72 h)
5	96 h	96:00	X	X (72-96 h)
6	120 h	120:00	X	X (96-120 h)
7	144 h	144:00	X	X (120-144 h)
9	192 h	192:00	X	
11	240 h	240:00	X	

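### Part A renal clearance divides urine collected to 144 h by a plasma AUC that can run to 192 or 240 h, so CLr is too low in any subject still quantifiable after 144 h

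*SAP*

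**What the plan says.** SAP Table 5 (section 15.1.2.2) gives CLr as Ae(0-T) divided by AUC(0-T). It describes Ae(0-T) as "Total amount of drug excreted unchanged into urine to time t obtained by adding the amounts excreted over each collection interval". A separate row, Ae, is "Total amount of drug excreted unchanged into urine to last time obtained by adding the amounts excreted over each collection interval". The missing-data rule for Ae(0-T) is "Parameter will be missing if data is missing for any prior individual time interval".

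SAP Table 4 defines AUC(0-T) as "Area under the concentration-time curve (time 0 to time of last quantifiable concentration" and takes it from the WinNonlin AUClast output.

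The Part A schedule is in SAP Appendix 3, "Table 8 Pharmacokinetic Sampling Schedule; Part A". Plasma is drawn at 144, 192 and 240 h, and the last urine interval is 120-144 h. Protocol Table 11 has the same last interval. Protocol 8.1.1 explains why collection stops there: "discharge from the CRU on Day 7 (144 hours post-dose). Subjects will return for ambulatory assessments on Days 9 and 11".

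SAP section 15.2.4 does not truncate the AUC at the end of urine collection. Protocol 8.5.3 lists renal clearance without a formula, so Table 5 is the only working definition.

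**The concern.** Renal clearance is an amount excreted over a window divided by the exposure over that same window. Here the two windows are set by different things: the numerator by when collection stopped, the denominator by assay sensitivity in plasma. They share the letter T, but nothing ties them together.

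Once the last quantifiable plasma time passes 144 h, they cannot match, because no urine exists beyond 144 h. The error then always has the same sign, so averaging over subjects does not remove it.

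When the last quantifiable time is before 144 h, a matched calculation is possible. The separate row for the total amount suggests that Ae(0-T) is meant as a running sum. Table 5 still does not say which t to use. CLr would be overstated only if urine were summed to 144 h regardless.

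At stake is the accuracy of a reported parameter. Renal clearance is listed for Part A under the primary endpoints in protocol 9.3.1 and is to be summarized by treatment. The error could differ between doses if the last quantifiable time does, but the documents do not establish a dose trend.

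**Working it through.** The plan states no CLr value or bias figure, so there is none to reproduce.

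**Inputs**
- Last urine time: 144 h (SAP Table 8, protocol Table 11).
- Later plasma times: 192 h and 240 h (same tables).
- Half-life: "anticipated terminal half-life of BMS-986251 of approximately 40 hours" (protocol 8.1.1).
- Assumptions: renal clearance constant over time; mono-exponential decline in the base case.

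**Formula.** With constant renal clearance, Ae(0-144) = CLr × AUC(0-144). Table 5 divides this by AUC(0-T), so

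reported CLr / true CLr = AUC(0-144) / AUC(0-T).

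For mono-exponential decline with half-life h, AUC(0-T)/AUC(INF) = 1 − 2^(−T/h).

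**At h = 40 h**
- AUC(0-144): 1 − 2^(−3.6) = 0.9175
- AUC(0-192): 1 − 2^(−4.8) = 0.9641
- AUC(0-240): 1 − 2^(−6) = 0.9844
- Last quantifiable time 192 h: 0.9175/0.9641 = 0.952, so CLr is 4.8% too low.
- Last quantifiable time 240 h: 0.9175/0.9844 = 0.932, so CLr is 6.8% too low.

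**Other half-lives (assumed)**

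| Half-life | Share of AUC(INF) by 144 / 192 / 240 h | CLr too low, last time 192 h | CLr too low, last time 240 h |
|---|---|---|---|
| 20 h | 0.9932 / 0.9987 / 0.9998 | 0.6% | 0.7% |
| 30 h | 0.9641 / 0.9882 / 0.9961 | 2.4% | 3.2% |
| 40 h | 0.9175 / 0.9641 / 0.9844 | 4.8% | 6.8% |
| 60 h | 0.8105 / 0.8912 / 0.9375 | 9.0% | 13.5% |
| 80 h | 0.7128 / 0.8105 / 0.8750 | 12.1% | 18.5% |

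**Other profile shapes, all at 40 h**
- One-compartment oral absorption, rate constant 0.3 to 2 per hour: 4.9-5.1% at 192 h and 6.9-7.2% at 240 h.
- Linear-up/log-down AUC on the scheduled times (absorption rate constant 1 per hour): 4.9% and 6.9%.
- Half of AUC(INF) in an early phase that is over by 144 h (assumption): the ratio becomes (1 − 0.5 × 0.0825)/(1 − 0.5 × 0.0359) = 0.976 at 192 h and (1 − 0.5 × 0.0825)/(1 − 0.5 × 0.0156) = 0.966 at 240 h. CLr is 2.4% and 3.4% too low.

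**Can the condition occur?** The documents give no lower limit of quantification. At 40 h, the concentration at 144 h is 2^(−3.6), about 8% of the back-extrapolated starting value. As an illustration only, under dose proportionality the step from 2 mg to 30 mg extends the last quantifiable time by 40 × log2(15) = 156.3 h. The 30 mg dose would then be quantifiable at 192 h if 2 mg were quantifiable to about 36 h (192 − 156.3 = 35.7), and at 240 h if 2 mg were quantifiable to about 84 h (240 − 156.3 = 83.7).

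**The case against.** **The label T could be read strictly.** If T is the plasma time and exceeds 144 h, Ae(0-T) does not exist, and a programmer might return CLr as missing rather than low. Table 5 does not say this. Its rule concerns data missing in earlier intervals, and no interval is scheduled after 144 h. On that reading CLr is lost for the subjects with the longest profiles, so the definition still needs correcting.

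**The number affected is unknown and could be zero.** This stands. There is no assay limit and there are no observed concentrations. Urine summaries are made only if applicable (SAP 15.2.4). Protocol 8.5.3 says of the urine assessment "which may be limited to the higher dosed cohorts in Part A and B"; those are also the cohorts in which late quantifiable plasma is more likely.

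**The error is small against the noise.** This also stands. With six active subjects and an assumed between-subject CV of 20-40%, the standard error of a mean is about 20/√6 = 8% to 40/√6 = 16%, more than the 40 h bias. But the bias is systematic and avoidable, which sampling noise is not.

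**No decision in the study rests on CLr.** This is correct. The SAP plans no formal hypothesis testing, dose proportionality uses plasma parameters only, and the study was terminated before the SAP was written. The consequence is confined to the reported renal clearance.

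**A schedule row seems to show urine out to 240 h.** In the text available, the SAP Appendix 2 urine row does, but the columns of that table are visibly displaced. The explicit interval tables and the 144 h discharge agree on 144 h.

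**Conclusion.** The concern holds. As written, Table 5 understates CLr for every subject with quantifiable plasma at 192 or 240 h. The direction follows from the definitions and the schedule, given constant renal clearance. The size depends on the profile: 4.8% to 6.8% at the anticipated 40 h half-life with mono-exponential decline, 2.4% to 13.5% over assumed half-lives of 30 to 60 h, and 2.4% to 3.4% at 40 h if half of the exposure falls in an early phase. There is no bias when the two windows match. How many subjects are affected cannot be determined from the documents. This is a modest error in a descriptive parameter, and it should be corrected because the correction is easy.

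**What to change.** In Table 5, define CLr = Ae(0-t*)/AUC(0-t*), where t* is the end of the last urine interval that falls at or before the last quantifiable plasma time, with that interval and all earlier ones complete. t* is then at most 144 h. This also settles which t applies when plasma becomes unquantifiable before 144 h. Under the same assumptions the bias is zero. At 40 h, CLr rises by a factor of 0.9641/0.9175 = 1.051 (last quantifiable time 192 h) or 0.9844/0.9175 = 1.073 (240 h) relative to the current formula.

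The cost is a revised definition in Table 5 and one partial AUC per subject. Each urine interval end (12, 24, 48, 72, 96, 120 and 144 h) has a scheduled plasma sample, so no sampling is added. Two details should be stated:
- Actual times are used, and the protocol allows ±5% (±7.2 h at 144 h). The SAP should say how the AUC is interpolated to the actual end of urine collection.
- Some urine drops out of CLr. With a last quantifiable time of 36 h, t* is 24 h and the 24-48 h collection is not used for CLr. It still counts towards Ae and Fe.

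A clerical point in the same table: Ae is computed in ng while the dose is in mg, so the Fe row should show the conversion, Fe = Ae(ng)/(dose(mg) × 10^6) × 100.
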